Secondary Clinical Endpoints	
Post-transplant outcomes including:
 
 1. Incidence of chronic allograft dysfunction, listing for retransplantation and death during the follow-up period, which will be a minimum of 12 months post-transplant; 2. Incidence of Primary Graft Dysfunction; 3. Incidence of Grade A Acute Rejection during the follow-up period, which will be a minimum of 12 months post-transplant; 4. Incidence of Antibody Mediated Rejection during the follow-up period, which will be a minimum of 12 months post-transplant; 5. Incidence of tacrolimus variability threshold during the follow-up period, which will be a minimum of 12 months post-transplant; 6. Percentage of participants meeting tacrolimus variability threshold who complete tacrolimus variability intervention; 7. Magnitude of change in standard deviation of tacrolimus levels following intervention. 
Post-transplant safety outcomes including:
 
 1. Incidence and severity of infection episodes;

	2. Serious adverse events related to rituximab.
Secondary Mechanistic Endpoints	
 1. Incidence and kinetics of DSA and autoantibodies, specifically Collagen V (CoIV) and k-alpha-1 tubulin ($\kappa\alpha 1T$); 2. Frequency, kinetics, phenotype and function of peripheral B cells; 3. Frequency, kinetics and cytokine profiles of allo- and auto reactive T cells; 4. Incidence and quantity of B cells and B cell proximity to other cells in the graft tissue.
Accrual Objective	50 randomized pediatric lung transplant recipients
Study Duration	
4.5 years (3.5 year accrual + 1-4.5 year follow-up period)
 
All participants will be followed for a minimum of 1 year post-transplant. Participants will continue follow up visits (up to 4.5 years post-transplant) until the last participant completes 1 year of follow-up.

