8.4. Study Assessments

Subjects enrolled in this study will be followed for a minimum of 12 months post-transplant. Follow up visits will continue as detailed in Appendix 1 until the last participant completes 12 months of follow up (up to 54 months). Subjects may have blood and BAL samples collected at the following timepoints post-transplant:

- Transplant/Randomization-Day 0
- Day: 12
- Weeks: 4-6
- Months: 2, 3, 6, 9, 12, 18 and 24

Clinical safety will be monitored through routine physical examinations and appropriate laboratory assessments. During this period participants will have repeated clinical/laboratory evaluations, as specified in the Schedule of Events (Appendix 1, Schedule of Events- Recipient).

Assessments for the development of adverse events, serious adverse events, infections, rejections, death, PTLD, relisted for transplant or re-transplantation and hospitalizations will be completed at each study visit. All events will be reported using a designated electronic case report form (eCRF).

Chronic allograft dysfunction, relisting for transplant and death data will be collected up to 54 months post-transplant.

Protocol Biopsies

Transbronchial biopsies will be performed routinely as part of standard of care. The histologic evaluations from routine biopsies at day 12, week 4-6, month 3, month 6, month 12, month 18, and at the time of a symptomatic episode will be evaluated by the local pathologist and interpretations recorded on electronic case report forms (eCRFs).

Tacrolimus Standard Deviation Marker

Variability of tacrolimus will be monitored continuously starting 3 months post-transplant, using the calculation of the degree of fluctuation of tacrolimus blood levels over time, described by the standard deviation (SD) of tacrolimus levels.⁸² All outpatient levels obtained at least 3 months post-transplant will be used. In order to ensure the validity of tacrolimus trough levels, clinical sites will agree on quality control measures for obtaining trough levels. A rolling SD will be calculated for every patient using 1-year of tacrolimus levels (at least 3 trough levels). A SD of 2.0 or more (Shemesh et al. manuscript in preparation), an undetectable level or the absence of a tacrolimus trough level for 3 months will trigger a phone call among the site coordinator, the participant, parent(s)/guardian(s) and trained personnel at ISMMS to address barriers to adherence.

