Individuals who meet the criteria listed below will not participate in the phone calls for the tacrolimus standard deviation marker:

1. Inpatient status
2. Any condition that, in the opinion of the investigator, may impact the quality or interpretation of the data obtained from the intervention.

The frequency of the calls is described in the table below.

Timepoint (following SD of 2.0 or more or undetectable level)	Call Frequency
Month 1	Weekly
Month 2	Monthly
Month 3-Month 24	Every other month

Table 10: Tacrolimus Standard Deviation Marker Call Schedule

Per the center clinician's discretion, calls may be escalated to 2 times per week for up to 1 month at any time during the intervention.

After one month, calls may revert to a weekly schedule for the following reasons:

- Participant discloses continuing non-adherence during the call;
- The most recent trough level is “undetectable”;
- The parent/guardian and/or team are concerned about ongoing non-adherence;
- A deterioration in medical outcomes as determined by the Center that is not explained by physiological factors;
- Per the clinical discretion of the call center staff member (i.e., the call center and parents/guardians are working on a remedy to an identified barrier).

The team at the call center will determine when the participant will return to the schema outlined in **Table 10**.

With the consent of the participant, information obtained during the intervention will be shared with the participant’s parent(s)/guardian(s) and clinical team.

Neurological Assessment

All participants who receive at least 1 dose of Rituximab (Rituxan®) or placebo will undergo a screening neurological exam at the time points specified in Appendix 1. Subjects who have objective findings will be evaluated by their local Neurology consult service.

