11.1. Participant Completion

All participants will be followed for a minimum of 12 months and up to 54 months after transplantation.

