7.3.1. Post-transplant Clinical Endpoints

Variable: Secondary incidence endpoints including:

- Chronic allograft dysfunction, defined as indicated for the primary endpoint
- Listing for re-transplant, defined as indicated for the primary endpoint
- Death, defined as indicated for the primary endpoint
- Primary Graft Dysfunction (PGD), defined at 0, 24, 48, and 72 hours post-transplant per Section 7.5.4 of the protocol
- Grade A Acute Rejection, reported locally as defined in Section 7.5.1 of the protocol

- Antibody Mediated Rejection of Grade II or III, reported locally as defined in Section 7.5.2 of the protocol
 - Additionally, if the data allow, AMR will be evaluated according to the 2016 ISHLT consensus guidelines published in the Journal of Heart and Lung Transplantation.

Analysis: For each of the above incidence endpoints, the proportion of subjects with events will be reported by treatment group with a corresponding 90% confidence interval, and for PGD and the rejection endpoints the treatment groups will be compared using a Chi-square or Fisher's Exact test. The incidence of grade 2 or higher PGD will be summarized overall and at each of the 4 time points separately. Additionally, for acute rejection and antibody mediated rejection, number of events per person time (e.g., year) will be estimated.

An example of SAS code to be used:

```
Proc freq;  
  tables treatment_group * endpoint / chisq measures cl alpha=0.1;  
run;
```

Variable: Incidence of meeting the tacrolimus variability threshold

Analysis: Among subjects who have at least 3 outpatient tacrolimus trough levels collected that are at least 3 months (i.e., greater than or equal to 3 months) post-transplant, an estimate of the standard deviation of tacrolimus levels will be produced for each subject. This estimate will be a rolling estimate (continually re-assessed) and may use up to 1 year worth of trough levels at any given time. The proportion of subjects with an estimated standard deviation at any time of 2.0 ng/mL or greater will be reported with a corresponding 90% confidence interval.

Variable: Incidence of completion of the Tacrolimus Variability Intervention (TVI)

Analysis: Among subjects who qualified for and agreed to participate in the TVI, the proportion of subjects who complete the intervention will be reported with a corresponding 90% confidence interval.

Variable: Magnitude of change in standard deviation of tacrolimus levels following intervention

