Analysis: Among subjects who qualified for and agreed to participate in the TVI, the change in standard deviation of tacrolimus levels following the TVI will be examined. More specifically, a paired t-test will be carried out using the pre-intervention and post-intervention estimates of the standard deviation. An estimate of the mean difference between pre- and post-intervention standard deviation with a corresponding 90% confidence interval and p-value will be produced.

The value used for pre-intervention may be the same estimated standard deviation which qualified the subject for the TVI; however, if additional tacrolimus levels are recorded for a subject prior to their re-affirmation of consent for TVI participation, all outpatient tacrolimus levels in the year prior to commencement of the TVI will be used for estimating the pre-intervention standard deviation.

Likewise, the standard deviation value used for post-intervention will be estimated using all outpatient tacrolimus levels collected in the 180 days following completion of the TVI.

All estimates of the standard deviation pre- or post-intervention will adhere to the same conditions described earlier, which mandate at least 3 outpatient tacrolimus levels collected at least 3 months post-transplant.

Additionally, the change in standard deviation will be analyzed using the same paired t-test approach for pre-intervention vs. 180 days post-enrollment into the TVI, providing an assessment of change during the intervention.

Furthermore, attempts will be made to identify a set of “control” subjects for descriptive comparisons to subjects who enrolled and completed the TVI. These “control” subjects will at a minimum consist of subjects who qualified for but did not enroll in the TVI, and may be supplemented with subjects whose standard deviation exceeded 2.0 ng/mL but were not flagged due to enrollment in the TVI having been terminated. No formal statistical comparison of these two sets of subjects is planned.

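### TVI completion is undefined and study close is not handled, although a 24-month call schedule does not fit within 12 to 54 months of follow-up for many triggered children

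*SAP*

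**What the plan says.** Protocol 8.4 sets the trigger: "Variability of tacrolimus will be monitored continuously starting 3 months post-transplant". An SD trigger needs at least three levels; an undetectable level, or three months without a level, also triggers. Table 10 counts its months from the trigger, and its last row, for calls every other month, is "Month 3-Month 24".

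On duration, Protocol 11.1 states: "All participants will be followed for a minimum of 12 months and up to 54 months after transplantation". Protocol 8.4 adds that visits stop for everyone once the last child reaches 12 months.

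SAP 7.3.1 has three relevant analyses:

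- **Completion.** Among children who met the trigger and consented to the calls, "the proportion of subjects who complete the intervention will be reported with a corresponding 90% confidence interval". Completion is not defined. The denominator is not limited by how long a child could be followed, and there is no censoring rule.
- **Main change in SD.** A paired comparison of the SD before the TVI with one "estimated using all outpatient tacrolimus levels collected in the 180 days following completion of the TVI". At least three levels are required.
- **Additional change in SD.** The same paired comparison, with the later value taken at 180 days after TVI enrolment.

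The SAP also mentions children who exceeded the threshold but were not flagged because TVI enrolment had been terminated. It gives no date.

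**The concern.** Secondary objective 3 is the feasibility of this phone intervention, and the completion percentage is the most direct answer to it. A child transplanted late in accrual can take every call offered and still not reach the end of a 24-month schedule, because the study closes first. A plain proportion gives such a child no category of its own. The figure then mixes acceptance of the calls with date of transplant, and a well-accepted intervention could be reported as hard to complete.

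The main change-in-SD analysis has the same difficulty with a further window added. It would rest on children triggered early in a long follow-up, who may be few in a trial of 50.

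**Working it through.** **Inputs from the documents.** Accrual 3.5 years and study length 4.5 years (Protocol Synopsis). Follow-up 12 to 54 months with a common stop (Protocol 11.1 and 8.4). Monitoring from month 3 and calls to month 24 after the trigger (Protocol 8.4, Table 10). Post-completion window 180 days, or 180/30.4375 = 5.9 months, with at least three levels (SAP 7.3.1).

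**Assumptions, not in the documents.** Accrual is uniform over 42 months. There are no deaths or dropout. TVI enrolment happens at the trigger, in month t. Completion means the end of Table 10.

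**The plan's own figure.** Maximum follow-up is 3.5 × 12 + 12 = 54 months, which agrees. The documents give no sample size or evaluable number for the TVI endpoints.

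**Limits that need no accrual assumption.**

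- Earliest end of the schedule: 3 + 24 = month 27.
- Earliest end of the full 180-day window: 27 + 5.9 = about month 33.
- Latest trigger that allows completion with 54 months of follow-up: 54 − 24 = month 30. For the full window: 54 − 24 − 5.9 = about month 24.
- A child followed for only 12 months cannot complete.

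**Shares under uniform accrual.** Follow-up F is uniform on 12 to 54, so P(F ≥ x) = (54 − x)/42. For t up to 12 every child is still followed at the trigger, and therefore:

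- cannot complete = (t + 12)/42
- three months after completion not reached = (t + 15)/42
- full 180-day window not reached = (t + 17.9)/42
- 180 days after TVI enrolment not reached = (t − 6.1)/42, or 0 if negative

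| Trigger month | Cannot complete | No 3 months after completion | No full 180 days after completion | No 180 days after TVI enrolment |
|---|---|---|---|---|
| 3 | 15/42 = 36% | 18/42 = 43% | 20.9/42 = 50% | 0% |
| 6 | 18/42 = 43% | 21/42 = 50% | 23.9/42 = 57% | 0% |
| 9 | 21/42 = 50% | 24/42 = 57% | 26.9/42 = 64% | 2.9/42 = 7% |
| 12 | 24/42 = 57% | 27/42 = 64% | 29.9/42 = 71% | 5.9/42 = 14% |

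The third column matters because the SAP asks for three levels, not 180 observed days.

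**Random trigger times.** With exponential delays from month 3 (median 1 to 12 months, simulated), 39% to 59% cannot complete and 53% to 73% lack the full window.

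**Accrual shape.** If accrual declines linearly (front-loaded), the share unable to complete is ((t + 12)/42)². If it rises linearly (back-loaded), the share is 1 − ((30 − t)/42)². At t = 6 these give (18/42)² = 18% and 1 − (24/42)² = 67%.

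**Definition of completion.** If six months of calls counted as completion, the share unable to complete is (t − 6)/42, or 0 if negative: 0% at months 3 and 6, and 6/42 = 14% at month 12. The share lacking the full post-completion window would be 7% at month 3 and 28% at month 12.

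**The case against.** Completion is never defined, so the 24-month length is a reading of the last row of Table 10. Under a six-month reading most of the loss disappears. The post-completion SD needs only three levels. TVI enrolment was closed at some point, which keeps late triggers out of the denominator. The SAP already plans an SD comparison that fits the study's length. The endpoint is secondary and carries no power claim. The protocol's endpoint is change following the intervention, so the SAP's main SD analysis follows the protocol.

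Most of this stands, and it rules out several stronger statements that a reader might infer:

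- *That children cut off by study close are counted as non-completers.* The SAP gives no rule for them. The defect is that they cannot be distinguished.
- *That a child needs 33 months of follow-up to be evaluable.* That is the earliest end of the full window, not a requirement of the SAP.
- *That about half of triggered children cannot be evaluated.* The share depends on assumed accrual and trigger times. It also applies only to the post-completion SD, not to the 180-days-post-enrolment SD.
- *That completion mostly measures date of transplant.* Refusal and dropout are assumed away here, so only a dependence on transplant date is shown.
- *That no child can complete, because Protocol 13.4.2 mentions a two-year follow-up period.* That phrase concerns censoring in the primary analysis and conflicts with the 12 to 54 months stated elsewhere.

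The objection does not supply a definition of completion or a rule for study close. That completion depends so heavily on an unstated definition is a reason to state one.

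**Conclusion.** The concern holds as a gap in the SAP. The full Table 10 schedule ends no earlier than about month 27, follow-up can be as short as 12 months, and the completion proportion makes no allowance for this.

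If completion means the end of Table 10, with uniform accrual and no deaths or dropout, 36% to 57% of children triggered between months 3 and 12 could not complete. The full post-completion window would be missing for 50% to 71%, or the post-completion SD for about 43% to 64% if three levels within three months are enough. By contrast, the window for the 180-days-post-enrolment SD is available for about 86% to 100% of the same children.

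The direction is firm under the 24-month reading; the size is not. Accrual shape alone moves the completion loss from 18% to 67% at a month-6 trigger. Closure of TVI enrolment would lower the loss by an unknown amount, while deaths and loss to follow-up would raise it.

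**What to change.** In SAP 7.3.1:

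1. Define completion explicitly against Table 10.
2. Report completion at a horizon that most triggered children can reach, for example the calls scheduled in the first six months after TVI enrolment.
3. Report 24-month completion only among children with at least 24 months between TVI enrolment and study close, or as a time-to-discontinuation estimate censored at study close.
4. Keep the post-completion SD as the protocol's endpoint and state how many children could contribute to it. Present the 180-days-post-enrolment SD beside it as a co-reported result.

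The cost is SAP wording; no visits, samples or calls are added. The censored estimate needs the date on which each child's calls stopped. The documents do not say how this is recorded, so it should be confirmed. There are two limits on interpretation: a short-horizon completion figure does not describe the full 24-month schedule, and the post-enrolment SD describes change during the intervention, not after it.

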7.3.2. Post-transplant Safety Endpoints

The safety sample will be used for analysis of these post-transplant safety endpoints.

Variable: Incidence and severity of infection episodes

Analysis: We will analyze each type of infection separately (bacterial, fungal, or viral, including RVI, CMV, and EBV), as well as for all types of infections combined. We will first determine the incidence of bacterial, fungal and viral infections in the rituximab and control groups using a combination of information from both the local, clinical site and the viral detection core laboratory. The presence of an infection at a given time point will be defined as follows:

- A local report of infection through either the organism specific CRF page or adverse event reporting;
- Presence of symptoms at the time of a study visit without a local report of infection but with a corresponding core lab identified infection.
 - All symptoms reported at the time of a study visit will be considered for any EBV and CMV infections identified by the core lab.
 - For any other infections identified in core lab NP and BAL samples, shortness of breath, new x-ray or other imaging finding, new supplemental oxygen requirement, cough with sputum, and decreased spirometry will be the only symptoms considered.

‘Incidence rate’ will be the number of infections per patient-month, and we will focus on the estimates and associated 90% confidence intervals for the ratio of such rates (RR), where $RR > 1.0$ indicates greater infection rates for rituximab. Of course, infection events are biologically related within patient, thus, relative to perfect independence of events, greater proportions of patients will experience more episodes of the same type of infection and greater proportions of patients will experience no episodes. Accordingly, Poisson regression models offset for months of follow-up and adjusted for overdispersion will be used to compare groups on the rate of each type of infection and any infection.

The severity of infection episodes will be determined by reconciling all infections, as defined above, against those infections which qualified for adverse event (AE) reporting. Since the protocol restricts AE reporting to only those events which meet NCI-CTCAE grading criteria of Grade 3 or higher, any infections not reported as an AE will be assigned a severity of Grade ‘<3’ (effectively combining Grades 1 and 2); all other infections will utilize the assigned CTCAE severity grade of the corresponding AE. The proportion of subjects within each severity grade will be reported by treatment group with a corresponding 90% confidence interval; treatment groups will be compared using a Chi-square or Fisher’s Exact test. This presentation will be repeated for the number of events divided by person time, where time is the same across severity groups.

Variable: Serious adverse events (SAEs) related to rituximab

Analysis: For all SAEs, assessment of the relationship to rituximab will be made by the DAIT medical monitor. The proportion of subjects with SAEs determined to be related to rituximab will be reported by treatment group with 90% confidence intervals, and treatment groups will be compared using Chi-square or Fisher’s Exact test.

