Rituximab is a chimeric mouse/human monoclonal antibody approved as early as 1997 for use in Non-Hodgkin's Lymphoma, Chronic Lymphocytic Leukemia, Rheumatoid Arthritis (RA) in combination with methotrexate in adult patients with moderately-to severely-active RA who have inadequate response to one or more TNF antagonist therapies, Wegener's Granulomatosis and Microscopic Polyangiitis in combination with glucocorticoids. Rituximab targets CD20, a cell surface expressed protein found immature, transitional, mature and memory B cells but is absent on antibody producing plasma cells. While its exact mechanism of action is not fully understood, multiple studies in adults with autoimmune diseases such as Systemic Lupus Erythematosus (SLE) or RA showed that rituximab markedly depletes CD19+HLA-DR+⁵⁷ and memory CD19+CD27+ B cells.⁵⁸ Switched memory B cells (CD27+IgD-) are relatively spared compared to CD27-IgD+ naïve B cells and CD27+IgD+ unswitched B cells.⁵⁸ Further in RA patients, responders to rituximab therapy showed a significant decrease in CD19+CD27+ memory B cells compared to non-responders indicating that response may be impacted by the subset of B cells affected.⁵⁷ One important consequence of rituximab-induced B cell depletion is that the host B cell repertoire repopulates over the ensuing 3-6 months. This reconstitution process appears to recapitulate B cell ontogeny, where immature B cells undergo negative selection on stromal cells in the bone marrow and emerge with a transitional phenotype into the periphery.⁵⁹ Transitional B cells, characterized by expression of CD38hiCD24hiIgD+CD27-CD10+/-,⁶⁰ require survival signals provided by the cytokines BAFF and APRIL and are key intermediaries in the development of the mature B cell repertoire. Evidence suggests that the transitional B cell population contains Breg and that transitional B cells are subject to mechanisms of self-tolerance in the periphery.

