Preliminary epidemiologic data revealed 23 of 31 (74%) of subjects had at least one positive viral specimen. The median time to virus-positive specimens was 65 days post-transplant (range 1-599). Rhino/enterovirus was recovered most frequently (40 episodes) compared to coronavirus (3), hMPV (1), influenza (2), RSV (2), adenovirus (1), parainfluenza (1). Rhino/enterovirus occurred throughout the year but the other viruses were detected in the winter/spring months. Along with previous infectious diseases epidemiology, we have the capacity to monitor for and respond to changes in the rates of infectious episodes in our patient population.

Development of Abs to HLA following Lung Transplant and its impact on the development of BOS:

Since 2006, the Washington University adult lung program and the [name] lab instituted serial analysis for development of Abs to donor mismatched HLA during the post-transplant period. All adult LTxR had negative donor cross-matches. Of 116 patients serially analyzed, 65 developed DSA (56%), with 52 in the first 90 days, again supporting our contention that early intervention will be required to prevent induction. To test the hypothesis that antibodies contribute to late graft injury, the [name] group used IVIG (500 mg/kg x 6 monthly doses) and rituximab (375 mg/m² x 1 dose) for desensitization. Of the 44 patients treated, 27 (61%) cleared the DSA, and 17 (39%) had persistent DSA. An additional 17 patients were treated with IVIG alone and 11 (65%) cleared the DSA. More importantly, patient and graft survival was significantly better in successfully desensitized patients (Figure 4) providing strong correlative evidence that DSA participate in the development of allograft injury.⁷⁸

[figure not shown]

Figure 4: Improved survival following clearance of DSA.

A critical role for Abs to self-Ags in the pathogenesis of BOS:

Among adult LTxR who developed DSA (n=57) and subsequently cleared DSA following Ab directed therapy (n=34), 9 patients nonetheless developed BOS. We detected persistence of Abs to self-Ags, CoIV and κ 1T in most of these individuals, strongly implicating pathogenic roles for Abs to self-Ags. As shown in **Figure 5**, the LTxR who cleared both Abs to HLA and self-Ags demonstrated improved freedom from BOS in comparison to patients that cleared only DSA but not Abs to self-Ags.

[figure not shown]

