For safety outcomes, we will analyze each type of infection separately (bacterial, fungal, or viral, including RVI, CMV, and EBV), as well as for all types of infections combined. We will first determine the incidence of bacterial, fungal and viral infections in the rituximab and control groups. 'Incidence rate' will be the number of infections per patient-month, and we will focus on the estimates and associated 90% confidence intervals for the ratio of such rates (RR), where $RR > 1.0$ indicates greater infection rates for rituximab. Of course, infection events are biologically related within patient, thus, relative to perfect independence of events, greater proportions of patients will experience more episodes of the same type of infection and greater proportions of patients will experience no episodes. Accordingly, a Poisson regression models offset for months of follow-up and adjusted for overdispersion will be used to compare groups on the rate of each type of infection and any infection.

Serious adverse events related to rituximab will be reported by their incidence rate per patient and per infusion with 90% confidence intervals. Adverse events will be summarized by treatment group, with 90% confidence intervals.

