Transplant Study Week					4-6																						
Transplant Study Month						2	3	6	9	12	18 ⁶	24 ⁶	25-54 ⁶														
Visit Number		00	01	02	03	04	05	06	07	08	09	10															
	load at post-transplant visits																										
Serology	HIV, HBsAg, HBCAb, HCV Ab (within 12 months of transplant)	X																									
Immunoglobulin Levels	IgG	X	X	X	X	X	X	X	X	X	X	X													X	X	
Pathology	Local Biopsy Histology Scoring (ISHLT), including c1q fixation and C4d			X	X		X	X	X	X	X														X	X	
	Rituximab or Placebo (375 mg/kg)		X	X																							
HUMORAL ANTIBODY CORE – WUSTL (PI: [name])																											
	Serum- Anti-HLA Ab, Non-HLA Ab, Crossmatch Testing	X	X	X	X	X	X	X	X	X	X	X														X	X
	Serum- Autoantibodies	X	X	X	X	X	X	X	X	X	X	X														X	X
MARKERS OF GRAFT INJURY CORE – WUSTL (PI: [name])																											
	Serum- Cytokine/Chemokine/GF				X		X	X	X	X	X	X														X	X
	Bronchoalveolar Lavage (BAL) – Supernatant for Cytokine Analysis		X	X	X		X	X	X	X	X															X	X
MOLECULAR IMMUNOLOGY CORE – ISMMS (PI: [name])																											
	Blood-mRNA Profiling, Gene Exp.				X		X	X	X	X	X	X															
	Bronchoalveolar Lavage – Pellet for Gene Expression Profiles		X	X	X		X	X	X	X	X															X	X
	RNA Sequencing for IgG VDJ Regions ([name], Emory)							X	X	X	X																
CELLULAR IMMUNOLOGY CORE – ISMMS (PI: [name])																											
	Blood- T and B Cell Phenotyping (Flow Cytometry)	X			X		X	X		X	X																X
	Bronchoalveolar Lavage –in Cell Preservative: Phenotyping B Cells		X	X	X		X	X	X	X	X															X	X
	T Cell Function (ELISPOT) and Plasma to Archive	X						X		X	X																X
IMMUNOHISTOCHEMISTRY CORE –ISMMS (PI: [name])																											
	Immunohistochemistry: CD4, FoxP3, CD20 and CD8, CD20 and CD68: (5 unstained slides: Minimum of 3 slides prepared with 2 sections each representative of more than one tissue section)			X	X		X	X	X	X	X															X	X
VIRAL DETECTION CORE –WUSTL (PI: [name])																											
	Bronchoalveolar Lavage – Whole specimen for Viral Detection		X	X	X		X	X	X	X	X															X	X
	Nasal Swab-Viral PCR		X	X	X		X	X	X	X	X															X	X
	Whole Blood Quantitative Viral Studies (CMV/EBV)	X	X	X	X	X	X	X	X	X	X	X														X	X

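### The infection comparison is one rate ratio over 12 to 54 months, so an excess confined to the months after rituximab would be diluted towards 1; period-specific ratios should be pre-specified beside it

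*SAP*

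**What the plan says.** SAP 7.3.2 and Protocol 13.4.4 define the infection measure in the same way: the incidence rate "will be the number of infections per patient-month". The arms are then compared by a rate ratio with a 90% confidence interval, and "Poisson regression models offset for months of follow-up and adjusted for overdispersion will be used to compare groups". This is done for bacterial, fungal and viral infection (including respiratory virus, CMV and EBV) and for all infections together. Neither section has an early window, a time term or a treatment-by-period term.

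The severity comparison later in SAP 7.3.2 also pools all follow-up. It compares the proportion of subjects in each severity grade by chi-square or Fisher's exact test, then repeats the presentation per person-time.

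On timing, the documents say:
- Follow-up (Protocol 11.1): "All participants will be followed for a minimum of 12 months and up to 54 months after transplantation".
- Dosing (Protocol 6.1.1.2, SAP 6.2): two infusions, on day 0 and on day 12 within 2 days either way.
- B cells after rituximab (Protocol 2.1): "the host B cell repertoire repopulates over the ensuing 3-6 months".
- Later risk (Protocol 5.1): in some cases viral infections appeared up to one year after rituximab was stopped.
- Precursor study (Protocol 2.4): "The median time to virus-positive specimens was 65 days post-transplant", with a range of 1 to 599 days.

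For the primary endpoint, Protocol 13.4.2 plans to examine whether the effect of rituximab is limited to early or late follow-up. There is no counterpart for infections.

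**The concern.** The exposure is short and the averaging period is long. If rituximab raises infection risk mainly while B cells are depleted, the excess falls in roughly the first 6 to 12 months, while most person-months come later. A model with a treatment term and an offset reports the average over all of them.

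Safety and tolerability form a secondary objective (Protocol 1.3), and the hypothesis in Protocol 1.1 claims benefit without loss of safety. A pooled ratio modestly above 1, with an interval spanning 1, could be read as reassurance even though infections had doubled during the months that matter most for this drug. With no period analysis pre-specified, a later look at early infections would fall under SAP 7.5, which allows only unspecified exploratory work.

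**Working it through.** The documents give no infection rate, assumed ratio or power for this comparison, so there is no planned figure to reproduce. The follow-up span is consistent: 3.5 years of accrual plus 1 year is 4.5 years, or 54 months, with a minimum of 12.

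**Inputs from the documents:** follow-up of 12 to 54 months, 25 children per arm (50 at 1:1), last dose about day 12, repopulation over 3 to 6 months, some viral infections up to 12 months.

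**Assumed inputs:** a true early rate ratio of 2, falling to 1 afterwards; mean follow-up of (12 + 54)/2 = 33 months (uniform accrual, no death or loss); an early background rate k times the later rate, with k from 1 to 3.

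**Formula.** With a log link, an offset and a treatment term only, the estimate is events per person-month in one arm divided by the same in the other. If the excess lies in the first w months and every child completes them, then

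pooled RR = 1 + (early RR − 1) × f, with f = k·w / (k·w + 33 − w),

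where f is the share of control-arm infections that fall in the window.

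| k | w = 6 months | w = 12 months |
|---|---|---|
| 1 | f = 6/33 = 0.18, RR 1.18 | f = 12/33 = 0.36, RR 1.36 |
| 2 | f = 12/39 = 0.31, RR 1.31 | f = 24/45 = 0.53, RR 1.53 |
| 3 | f = 18/45 = 0.40, RR 1.40 | f = 36/57 = 0.63, RR 1.63 |

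If deaths and losses cut mean follow-up to 24 months, the 6-month results become 1.25, 1.40 and 1.50 (f = 6/24, 12/30, 18/36). The dilution is milder but remains.

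**What an early window would show.** In simulations with 25 per arm, follow-up was uniform on 12 to 54 months, between-child (gamma) variance was 0.5, and intervals were 90% from an overdispersed Poisson model (3,000 runs per setting). The excess was set to months 0-6 with a ratio of 2. The chance that the lower limit exceeds 1 was:

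| Later rate per month | k | Whole follow-up | Months 0-6 |
|---|---|---|---|
| 0.05 | 1 | 16% | 39% |
| 0.05 | 3 | 34% | 71% |
| 0.10 | 1 | 19% | 59% |
| 0.10 | 3 | 39% | 82% |

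These rates and the variance are also assumptions. The window here matches the true risk period exactly. If the excess lasted only 3 months, a 0-6 month ratio would itself be diluted, to (2 × 3 + 3)/6 = 1.5 with a flat background.

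**Interval width.** Take 0.05 per month and k = 1, before any overdispersion. Months 0-6 give 25 × 6 × 0.05 = 7.5 expected placebo events and 15 on rituximab. The standard error of the log ratio is √(1/7.5 + 1/15) = 0.447, so a ratio of 2.0 has a 90% interval of about 0.96 to 4.17. Whole follow-up gives 25 × 33 × 0.05 = 41.25 and 48.75 events, a standard error of 0.212, and a ratio of 1.18 with an interval of about 0.83 to 1.67. The early interval is wider but is centred on the early effect.

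**The case against.** The strongest reply is that total infection burden is a legitimate safety question, and the planned ratio estimates it without bias. That stands: the ratio is not wrong, it answers a different question. Early harm also has some oversight, through at least yearly DSMB review and the hospitalised-infection stopping rule in Protocol 12.8.2. That rule, however, tests each arm against a fixed 40% threshold at any time of follow-up. It does not compare the arms early.

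The reply is right to resist several stronger readings that a reader might draw:
- *This ratio is the only infection comparison between arms.* It is not: SAP 7.3.2 also compares severity, and SAP 8.2 tabulates adverse events by arm. None of these is split by time, so they do not fill the gap.
- *Thinner late sampling makes the dilution worse.* Appendix 1 schedules items such as "Nasal Swab-Viral PCR" only to month 18, and blood CMV/EBV testing to month 24. Late person-time is similar in both arms and cancels in expectation, so missing late events raises the early share and moves the pooled ratio towards the early one. With half of late infections detected and w = 6, k = 2, it is (24 + 13.5)/(12 + 13.5) = 1.47 rather than 1.31. Unscheduled symptomatic visits (Protocol 8.5) and local reports also continue.
- *The infection effect ends at 6 months.* Repopulation is not a proven end of risk; Protocol 5.1 points to up to a year, hence the 12-month column.
- *Months 0-6 should replace the planned comparison.* Protocol 7.2.2 gives CMV prophylaxis for at least 6 months whenever donor or recipient is seropositive, so a 0-6 month primary window could miss a delayed CMV signal.

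**Conclusion.** The point holds as a gap in what is pre-specified, not as an error in the model. Whenever an excess is confined to a window shorter than follow-up, the planned ratio lies closer to 1 than the early ratio; that direction follows from the algebra.

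The size is not fixed by the documents. On the stated assumptions, a true early ratio of 2 appears as about 1.18 to 1.40 for a 6-month excess and 1.36 to 1.63 for a 12-month excess. The day-65 median for virus-positive specimens hints at front-loading, which favours the upper part of each range. It is preliminary, concerns viral specimens only, and depends on when samples were taken.

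A reader might go further and infer that the trial will report no infection harm. The documents do not support that: Protocol 13.4 focuses on estimates and 90% intervals, so a ratio of 1.3 or 1.4 would be shown as above 1. The risk lies in interpretation, if the pooled ratio is taken alone as evidence that early infection was not increased. This is a cheap improvement that should be made, not grounds to replace the planned analysis.

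**What to change.** In SAP 7.3.2, keep the overdispersed Poisson model and the whole-follow-up ratio, and add:
- Period-specific rate ratios with 90% intervals for months 0-6, 6-12 and after 12, from period and treatment-by-period terms that allow for repeated periods within a child. Report these for any infection and, where counts allow, for bacterial, fungal and viral infection.
- A note that CMV is to be interpreted with the 6-12 month period, because prophylaxis covers at least the first 6 months for seropositive donor-recipient pairs.
- A statement that absence of infection harm will not be concluded from the pooled ratio alone.

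Restricting core-laboratory person-time to the scheduled sampling period is not needed to cure the dilution.

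The cost is SAP wording and one derived period variable, using infection dates already collected. The period-specific intervals are wider. Four infection groupings over three periods make 12 ratios, some of which may not be estimable with 25 children per arm, so any infection should carry the interpretation.
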